9.2. Clinical Laboratory Measurements

9.2.1. Pregnancy Test

A human chorionic gonadotropin (HCG) urine pregnancy test will be obtained from female subjects who are of childbearing age prior to their participation in the study at Screening, and again on Visit 2 before IMP administration (or on the day prior to IMP administration).

10. EVALUATIONS BY VISIT

10.1. Visit 1 –Screening

Screening to take place following SoC MRI brain scan and up to 28 days before Visit 2. Visit 1 – Screening may be performed at Day -1 (1 day prior to Visit 2 PET scan) only if next-day delivery of the ¹⁸F-fluciclovine dose is confirmed by the site.

1. Review the study with the subject (subject's LAR) and obtain written informed consent and HIPAA authorization and assent, if appropriate.
2. Assign the subject a unique subject number.
3. Record demographic data.
4. Record medical / disease history.
5. Record concomitant medications.
6. Record histopathological confirmation of the primary tumor or a metastatic site within 4 years of Screening.
7. Record previous cancer treatments for primary tumor (and other previous cancers, if applicable).
8. Record previous diagnoses and treatments for brain metastases.
9. Collect and review prior pre-treatment (if available), post-treatment and current SoC MRI brain scans as needed for the investigator to confirm eligibility. Upload MRI images to the central imaging core laboratory and annotate reference lesion, measure reference lesion, and annotate other equivocal lesions.
10. Record or assess ECOG performance status. A standard of care ECOG assessment may be recorded as the Screening ECOG if the assessment was performed within 28 days of Screening.
11. Perform urine HCG pregnancy test (female subjects of child-bearing potential only).
12. Confirm eligibility against the inclusion / exclusion criteria.
13. Investigator records the prospective Diagnostic Management Plan as noted following SoC MRI.
14. Schedule ¹⁸F-fluciclovine PET scan and order IMP for delivery on day of PET scan.
15. Schedule subject for Visit 2 (IMP + PET) to occur within 42 days of the SoC MRI, and provide the subject with ¹⁸F-fluciclovine PET scan preparation instructions (see [Section 11.1](#)).

The reference lesion is defined as the lesion which is:

- a. Equivocal for recurrent metastasis on SoC MRI (according to inclusion criterion #7, see [Section 6.2](#)).
- b. Intended for SoC biopsy/neurosurgical intervention procedure (if planned). If >1 lesion is intended for biopsy/intervention, the largest of these lesions will be the reference lesion.
- c. Where clinical follow-up is planned, the largest of all equivocal lesions (if >1 is present) will be the reference lesion.

If >1 equivocal lesion is under evaluation as SoC, the on-site investigator will also annotate 'other equivocal lesions' on the SoC MRI brain scan, defined as follows:

- a. Equivocal for recurrent metastasis on SoC MRI (according to the same radiological criteria for a reference lesion per inclusion criterion #7, see [Section 6.2](#)).
- b. Where SoC biopsy/neurosurgical intervention procedure is planned, these are the other equivocal lesions pre-planned for biopsy/intervention.
- c. Where SoC clinical follow-up is planned, these are the other equivocal lesions pre-planned for SoC clinical follow-up.

10.2. Visit 2 - Day 1: IMP Administration and Dynamic PET Scan (1 to 28 days after Screening)

At Visit 2-Day 1, the following activities will be performed:

1. The subject will prepare for the ¹⁸F-fluciclovine PET scan according to preparation instructions (see [Section 11.1](#)).
2. Record any changes in concomitant medications and medical history since Screening (Visit 1).
3. Perform urine HCG pregnancy test (female subjects of child-bearing potential only) unless performed 1 day prior to IMP administration.
4. Confirm eligibility against the inclusion / exclusion criteria.
5. Perform assessment of vital signs with the subject resting at least 5 minutes prior to IMP administration. The vital signs should be collected between 5 to 60 minutes before the PET scan.
6. IMP + PET: Administer ¹⁸F-fluciclovine injection, followed by a dynamic PET scan of the brain. If the PET scan is performed on a PET/CT scanner, a CT scan of the brain will also be performed for attenuation correction.
7. Monitor and record any adverse events.
8. Perform assessment of vital signs with subject resting at least 5 minutes after PET scan. The vital signs should be collected between 5 to 60 minutes after the PET scan.
9. Upload ¹⁸F-fluciclovine PET brain scan to central imaging core laboratory.
10. Review of ¹⁸F-fluciclovine PET brain scan by the site investigator to identify potential additional PET lesions will be performed with the Visit 2 MRI scan (for anatomical reference).
11. Investigator updates Diagnostic Management Plan following review of ¹⁸F-fluciclovine PET brain scan.

10.3. Visit 2 – Day 1 or up to 3 days after ¹⁸F-fluciclovine Administration: On-Study MRI Brain Scan

Visit 2 on-study MRI brain scan should take place on the same day as the ¹⁸F-fluciclovine PET scan (Day 1) or up to 3 days after. Where applicable, it should take place before the Visit 4 – SoC biopsy/neurosurgical intervention.

1. Perform Visit 2 on-study MRI brain scan as outlined in [Section 11.5](#).

2. Upload Visit 2 on-study MRI brain scan to the central imaging core laboratory.
3. Review of ¹⁸F-fluciclovine PET brain scan (with Visit 2 MRI for anatomical reference) by site investigator to identify potential additional PET lesions, not previously reported on SoC MRI.
4. Confirm sites of reference lesion and other equivocal lesions on Visit 2 scans.

The on-site investigator will review the ¹⁸F-fluciclovine PET scan to identify and annotate potential additional lesions, not previously reported on SoC MRI (termed ‘additional PET lesions’). Additional PET lesions should be annotated only where judged suggestive of brain metastasis, warranting confirmation by clinical follow-up, biopsy or resection, according to SoC practice. Undertaking biopsy/resection of additional PET lesion(s) identified on the ¹⁸F-fluciclovine PET scan is at the discretion of on-site investigators. Moreover, an additional PET lesion should be discrete and spatially separate from known, pre-existing lesions. In particular, the following should not be annotated as Additional PET lesions: known pre-existing non-progressive lesions (considered at site level as stable or partially responding), ¹⁸F-fluciclovine activity contiguous with a known lesion (previously annotated or otherwise) and apparently incongruent with the lesion’s outline on correlating MRI, particularly where this may be reasonably explained by image registration.

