6.2. Inclusion Criteria

1. Male or female ≥ 18 years of age at Screening (Visit 1).
2. Eastern Cooperative Oncology Group (ECOG) performance status of 0-2.
3. Subject or subject's Legally Authorized Representative (LAR) is willing and able to provide written informed consent.
4. Previous history of solid tumor brain metastasis of any origin.
5. Histopathological confirmation of the primary solid tumor or a metastatic site within 4 years of Screening (Visit 1). Cancer of unknown primary is excluded.
6. Previous radiation therapy of brain metastatic lesion(s) completed at least 8 weeks before Screening. Form of radiotherapy may include stereotactic radiosurgery or whole brain radiotherapy, previously delivered as primary (initial) treatment, in the adjuvant setting (e.g., post-surgery), salvage setting (repeat radiation therapy), in or out of the context of previous or concurrent systemic treatments.
7. A reference lesion considered by the site investigator to be equivocal for recurrent brain metastasis, as determined by a recent^{*} SoC MRI brain scan^{**}, measuring ≥ 5 mm in longest diameter on contrast-enhanced MRI, and meeting one of the following radiological criteria:
 - a. $\geq 20\%$ increase in the longest diameter of the reference lesion on contrast-enhanced MRI relative to nadir^{***}, where the longest diameter at nadir is ≥ 10 mm
 - b. ≥ 3 mm increase in the longest diameter of the reference lesion on contrast-enhanced MRI relative to nadir, where the longest diameter at nadir is < 10 mm
 - c. a contrast enhancing lesion at site of previous radiotherapy following complete lesion response (CLR, defined as disappearance of the irradiated contrast enhancing lesion on contrast-enhanced MRI).

^{*}SoC MRI brain scan must be completed within no more than 42 days before study PET scan.

^{**}The SoC MRI brain scan must consist of conventional sequences, defined as:

- T_1 -weighted without and with contrast enhancement, and
- FLAIR and/or T_2 -weighted.

If SoC also includes advanced/investigational MRI sequences, including but not limited to perfusion, spectroscopy, diffusion weighted imaging, and susceptibility weighted imaging, trial entry is permitted as long as the other inclusion criteria are met.

***Nadir is defined as the smallest size after radiotherapy, measured by single longest diameter on an available contrast-enhanced MRI.

8. Subject requires further confirmatory diagnostic procedures to confirm brain MRI findings and is planned for:

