15.6.4. Clinical Utility

Clinical utility endpoints include the following, and will be analyzed as described:

- Number of days taken by the site to establish presence/absence of metastasis by clinical follow-up will be defined as the time from administration of ¹⁸F-fluciclovine to the date the presence or absence of metastasis is determined at site level. If the presence or absence of metastasis is not ascertained by the time the subject reaches the end of the follow-up or when the subject prematurely withdraws from the study, the subject will be censored on the date he/she withdraws from the study. Kaplan-Meier methodology will be used to handle the

censoring of the data, and to estimate the median time to establish presence/absence of metastasis.

- Proportion of subjects with additional metastases identified on ¹⁸F-fluciclovine PET but not on SoC MRI. The estimate of the percentage and the associated 95% 2-sided exact CI will be presented.
- Proportion of subjects whose prospective diagnostic management plan changes following ¹⁸F-fluciclovine PET, by comparing the diagnostic management plans before and after ¹⁸F-fluciclovine PET. The estimate of the percentage and the associated 95% 2-sided exact CI will be presented.

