Subjects with additional metastases identified on ^{18}F -fluciclovine PET but not on SoC MRI are those with at least one lesion with type = 'Additional PET Lesion' on the lesion annotation eCRF page, which has SoR = 'positive' according to the CTP. Lesions that are deemed to have SoR = 'indeterminate' by CTP will not be considered as additional metastases.

The estimate of the proportion of subjects and the associated 95% 2-sided exact confidence interval (Clopper-Pearson) will be presented.

7.4.4.4.3 Proportion of subjects whose prospective diagnostic management plan changes following ^{18}F -fluciclovine PET.

The proportion of subjects whose prospective diagnostic management plan changes following ^{18}F -fluciclovine PET will be established by comparing the diagnostic management plan of the reference lesion before and after ^{18}F -fluciclovine PET.

The intended diagnostic management plan on the reference lesion will be recorded at visit 1 as craniotomy, biopsy, biopsy in context of LITT, or clinical follow-up. At visit 2, post ^{18}F -fluciclovine PET, the diagnostic plan will be recorded again. If a different option has been chosen, or if there are any additional/new subject management activities planned then this will be counted as a change.

The estimate of the proportion of subjects and the associated 95% 2-sided exact confidence interval (Clopper-Pearson) will be presented.

7.4.4.5 *Inter-Reader / Intra-Reader Agreement (Blinded Image Evaluation)*

For inter-reader agreement, pairwise comparisons of the ¹⁸F-fluciclovine PET scan central reads for the 3 readers (i.e. Reader 1 vs Reader 2, Reader 1 vs Reader 3, and Reader 2 vs Reader 3) will be performed at the subject-level (i.e., reference lesion only) and also at the lesion-level (i.e., all lesions defined by site). The number and percentage of each combination of results (Positive [1st reader] / Positive [2nd reader], Positive/Negative, Negative/Positive, Negative/Negative) will be presented, along with the number and percentage of results in agreement and disagreement. Cohen's kappa statistic will be calculated and presented for each pairwise comparison of the 3 readers, with the corresponding 95% CI and p-value.

Similar statistics will be presented for intra-reader agreement (10% of subjects) – comparisons will be between the initial read vs re-read of a subset of PET scans for each reader.

7.4.4.6 *Sensitivity Analyses*

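### The baseline plan for the management-change endpoint is recorded 1 to 28 days before PET and not refreshed before dosing, so plan changes unrelated to PET are counted in the result

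*Protocol*

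**What the plan says.** Endpoint 4c is one of three measures listed under clinical usefulness (Protocol 5.2, item 4). Protocol 15.6.4 derives it "by comparing the diagnostic management plans before and after" the PET scan.

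- **Baseline record.** Protocol 10.1, step 13, at Visit 1: "Investigator records the prospective Diagnostic Management Plan as noted following SoC MRI". SAP 7.4.4.4.3 uses the same record; the plan for the reference lesion "will be recorded at visit 1 as craniotomy, biopsy, biopsy in context of LITT, or clinical follow-up".
- **Timing.** Protocol 10.1: "Screening to take place following SoC MRI brain scan and up to 28 days before Visit 2". Screening on the day before PET is allowed if next-day dose delivery is confirmed. Protocol 6.2, note to criterion 7: "SoC MRI brain scan must be completed within no more than 42 days before study PET scan".
- **Post-PET record.** Protocol 10.2, step 11: "Investigator updates Diagnostic Management Plan following review of" the PET scan. Step 10 has that review done together with the Visit 2 MRI.
- **Counting rule.** SAP 7.4.4.4.3: "If a different option has been chosen", or "if there are any additional/new subject management activities planned then this will be counted as a change". No reason for the change is asked for.

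Before the injection at Visit 2, Protocol 10.2 has the site update medications and medical history (step 2) and re-confirm eligibility (step 4). The plan is not among the items refreshed.

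**The concern.** A before-and-after comparison credits the intervening test with everything that happens between the two records. Here the first record can be up to four weeks older than the test. A plan may move in that time because of symptoms, patient preference, theatre scheduling or systemic disease. Such a move first becomes visible in the post-PET record and is scored as a change.

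Among the three usefulness measures, 4c is the only one about management; 4a is time to a site diagnosis and 4b is additional metastases. The trial has one arm, so no comparison group shows how often plans move without PET. If 4c is later cited as evidence that PET alters management, it will include an unknown amount of ordinary change.

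**Working it through.** The documents give no expected rate, target or power for 4c, so there is no stated figure to reproduce. The check is the order of the records, followed by an illustration under assumed rates.

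**1. Order of events**

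| Step | Source | Time relative to PET |
|---|---|---|
| SoC MRI | Protocol 6.2, criterion 7 | up to 42 days before |
| Plan recorded | Protocol 10.1, step 13; SAP 7.4.4.4.3 | 1 to 28 days before |
| Medications, history and eligibility refreshed; plan not | Protocol 10.2, steps 2 and 4 | same day, before dosing |
| PET reviewed with Visit 2 MRI | Protocol 10.2, step 10 | after |
| Plan updated | Protocol 10.2, step 11 | after |

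The study overview (Protocol 4.1) and the SAP design section (6.1) describe the same sequence. Neither document lists a plan entry between Visit 1 and the post-PET update.

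**2. Would the eligibility check catch a switch?** Criterion 8 is met by planned biopsy or neurosurgical intervention (8a) or by planned clinical follow-up (8b). A subject who moves from one to the other remains eligible, so step 4 need not record the move.

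**3. Illustration.** Let p be the probability that the plan changes after PET relative to the plan in force just before it. Let d be the probability that the plan changed between the Visit 1 record and PET for other reasons, independently of p. Neither value is in the documents; both are assumed.

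- If a drifted plan never returns to the Visit 1 option after PET: reported rate = 1 − (1 − p)(1 − d) = p + d(1 − p).
- If every PET-related change in a drifted subject restores the Visit 1 option: reported rate = p(1 − d) + d(1 − p) = p + d(1 − 2p). Here a real PET-related change is missed because the two records match.

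| p | d | PET always restores | PET never restores |
|---|---|---|---|
| 20% | 5% | 0.19 + 0.04 = 23% | 1 − 0.80 × 0.95 = 24% |
| 20% | 10% | 0.18 + 0.08 = 26% | 1 − 0.80 × 0.90 = 28% |
| 20% | 15% | 0.17 + 0.12 = 29% | 1 − 0.80 × 0.85 = 32% |
| 10% | 5% | 0.095 + 0.045 = 14% | 1 − 0.90 × 0.95 = 14.5% |
| 10% | 10% | 0.09 + 0.09 = 18% | 1 − 0.90 × 0.90 = 19% |
| 10% | 15% | 0.085 + 0.135 = 22% | 1 − 0.90 × 0.85 = 23.5% |

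The lower formula exceeds p whenever d > 0 and p is below 50%, so the bias is upward over the range shown.

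**4. Scale.** Take the planned 130 evaluable subjects. With no PET effect (p = 0) and d = 10%, about 13/130 would still be reported as changed, with an exact 95% CI of 5.4% to 16.5%. For 26/130 (20%) the interval is 13.5% to 27.9%. With p = 20% and d = 10%, the reported 26-28% therefore lies near that interval's upper limit.

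**The case against.** The strongest reply is that the plan claims no causation. 4c is worded as change following PET, is summarised with a confidence interval, and has no hypothesis, threshold or part in the success criterion. A reader might infer that the SAP classifies these changes as caused by PET. It does not; the attribution comes from the objective that 4c serves. That limits the point but does not answer it, because the objective is the added usefulness of PET and no rule separates out other causes.

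Other parts of the reply also stand:

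- The gap can be a single day, so weeks of drift is the upper end and will vary by subject.
- A reader might take 42 days as the exposure. That follows only if step 13 means the plan as it stood just after the SoC MRI. The wording can equally mean the plan in force at Screening, prompted by that scan, which limits the gap to 28 days.
- A reader might infer that other causes can never be identified afterwards. That is too strong: the history and medication updates made before dosing may leave a dated trace of some of them. The eCRF is not among the documents and may ask for a reason, although neither document uses one.
- PET must fall 1 to 21 days before a pre-planned procedure, so a site with surgery booked will be attending to the current plan. It is still not asked to record it.

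Finally, a pre-dose record would not isolate PET, because the updated plan also draws on the Visit 2 MRI. That is correct, and it limits what the fix achieves.

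**Conclusion.** The point holds as a weakness of one descriptive secondary endpoint. The 4c baseline is 1 to 28 days old at PET, is not refreshed before dosing, and is compared under a rule that accepts any change for any reason. Non-PET changes in that interval are included in the reported proportion.

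The size is unknown. The inflation of 3-4, 6-8 or 9-12 percentage points at a 20% PET-related rate rests entirely on assumed drift of 5%, 10% or 15% and on independence of the two kinds of change. It shrinks where Screening is close to PET. The documents do not support presenting any of these figures as an expected bias, nor treating the no-restoration formula as the result; it is the upper end of a range. The primary NPA and PPA analysis does not use the plan records and is unaffected.

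**What to change.** **Protocol 10.2 and both schedules of procedures.** Before step 6, add re-recording of the Diagnostic Management Plan for the reference lesion prior to IMP administration, with the same four options plus any other management activities then planned. The last item is needed because the SAP also counts new activities as a change.

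**SAP 7.4.4.4.3.** Compare the pre-dose record with the post-PET record for 4c. Report changes from Visit 1 to the pre-dose record in a separate row, which would also give a direct estimate of d.

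**Subjects already scanned.** Use the Visit 1 plan, show these subjects separately with the days from Visit 1 to PET, and describe the result as change following PET together with the Visit 2 MRI.

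**Cost.** One extra entry at a visit that already takes place, a minor amendment with the approvals in Protocol 17.2, an SAP revision, two cohorts for 4c, and possibly a lower 4c percentage. The contribution of the Visit 2 MRI remains and should be stated with the result.

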10.4. Visit 3 – Safety Follow-up (+1 to 3 days after IMP Injection/PET)

1. Clinical safety review by telephone call (or in person if same day as scheduled SoC biopsy, Visit 2 MRI, or other planned visit) to assess concomitant medications and AEs.
2. Record any changes in concomitant medications since Screening (Visit 1).
3. Record any AEs which have occurred during the safety reporting period (from the time of ¹⁸F-fluciclovine administration until 1 day post ¹⁸F-fluciclovine administration). For scheduling purposes, the subject may be contacted up to 3 days after IMP injection, but the assessment is to be limited to the first day after IMP injection only.

10.5. Visit 4 – SoC Biopsy/Neurosurgical Intervention (if applicable, pre-planned 1 to 21 days after IMP Injection/PET)

Where this visit is applicable, SoC biopsy/neurosurgical intervention should also take place after both the Visit 2 on-study MRI brain scan and Visit 3 Safety Follow-up.

1. Document neurosurgical procedure:
 - a. Record sites of reference lesion and other equivocal lesions which underwent SoC biopsy, and where applicable, ‘additional PET lesion(s)’, if performed.
 - b. Record sites of reference lesion and other equivocal lesions which underwent resection, and where applicable, ‘additional PET lesion(s)’, if performed.*
- c. If applicable, record neuronavigation system used for neurosurgical procedure.

* *Undertaking biopsy/resection of additional PET lesion(s) identified on the ¹⁸F-fluciclovine PET scan is at the discretion of the on-site investigators. The lesions should be judged suggestive of brain metastasis, warranting confirmation according to SoC practice. The subject will receive post-procedural management per institutional SoC.*

- d. Where biopsy was performed, upload image/screenshot of neuronavigation system depicting stereotactic coordinates of biopsy. Where resection was performed, upload image/screenshot of neuronavigation system depicting the surgical resection plan/approach (if neuronavigation was not used for resection, a representative screenshot of the post-procedure MRI demonstrating the resection cavity is suitable).
- e. Upload neurosurgical procedural report.
- f. Record any clinical factors associated with the neurosurgical intervention which impacted the type of procedure performed.

2. Label specimens with lesion ID as referenced by the imaging core laboratory study imaging platform on the previously annotated scans.
3. Process specimens per SoC and local laboratory standard practice. Histopathological report from SoC biopsy/neurosurgical intervention will be recorded.
4. Ship a representative set of specimens to the central laboratory per the Sample Processing Manual.

